2.2 Rationale

Norovirus is a rare and emerging viral disease of medical importance in the immunocompromised subject. *In vitro*, nitazoxanide has been shown to be active against Norovirus. Results from double-blind placebo-controlled studies demonstrate that nitazoxanide decreases the duration of illness in subjects with viral gastroenteritis. Small observational studies suggest that nitazoxanide results in prompt improvement in clinical signs of Norovirus-induced gastroenteritis. Further, nitazoxanide enhanced local production of interferon which may contribute to more rapid clearance of virus. Studies of nitazoxanide for the treatment of Norovirus has presented limited data on quantitative virology and its impact on viral load are less well defined. Further, there are limited data on the impact of nitazoxanide on host and viral changes that may facilitate control and clearance of Norovirus.

The present study is a phase 2 multi-center, prospective, randomized, double-blind study designed to assess the efficacy of nitazoxanide taken twice daily for 28 days compared to placebo for the treatment of Norovirus gastroenteritis in immunosuppressed transplant subjects. Given the safety of prolonged therapy with nitazoxanide⁽⁸⁹⁻⁹²⁾, lack of interactions with common post-transplant medications, putative antiviral activity and prolonged duration of viral shedding we are assessing 28 days of therapy. The longitudinal monitoring phase will provide useful information on the course of host and viral responses in subjects with chronic Norovirus infection with and without treatment.

There are 2 arms of the study:

Nitazoxanide Arm: All subjects age ≥ 12 years: 500 mg (one tablet) nitazoxanide by mouth twice daily with food for 28 consecutive days.

Placebo Arm: All subjects age ≥ 12 years: Placebo (one tablet) by mouth twice daily with food for 28 consecutive days.

2.3 Potential Risks and Benefits

2.3.1 Potential Risks

There are a number of potential risks associated with this study. Risk is primarily derived from the study agent and the protocol-mandated procedures.

Risks Associated with Nitazoxanide: As outlined in the package insert for the nitazoxanide, the compound has been extensively studied and utilized clinically in a wide range of clinical settings including limited data in transplant recipients. The safety of nitazoxanide was evaluated in 2177

HIV-uninfected subjects 12 months of age and older who received nitazoxanide Tablets or nitazoxanide for Oral Suspension at the recommended dose for at least three days. In pooled controlled clinical trials involving 536 HIV-uninfected subjects treated with nitazoxanide Tablets or nitazoxanide for Oral Suspension, the most common adverse reactions were abdominal pain, headache, chromaturia and nausea (>2%). Safety data were analyzed separately for 280 HIV-uninfected subjects' ≥ 12 years of age receiving nitazoxanide at the recommended dose for at least three days in 5 placebo-controlled clinical trials and for 256 HIV-uninfected subjects 1 through 11 years of age in 7 controlled clinical trials. There were no differences between the adverse reactions reported for nitazoxanide -treated subjects based upon age.

The following adverse reactions have been identified during post approval use of nitazoxanide. Because these reactions are reported voluntarily from a population of uncertain size, it is not always possible to reliably estimate their frequency or establish a causal relationship to drug exposure. The following is a list of adverse reactions spontaneously reported with nitazoxanide Tablets which were not included in clinical trial listings:

Gastrointestinal disorders: diarrhea, gastroesophageal reflux disease.

Nervous System disorders: dizziness.

Respiratory, thoracic and mediastinal disorders: dyspnea.

Skin and subcutaneous tissue disorders: rash, urticaria.

Risks Associated with Protocol-Mandated Procedures:

Blood Samples: Drawing blood from a vein may cause local pain, bruising, occasional light-headedness, fainting, and very rarely, infection at the site of the blood draw.

Buccal Swabs: Buccal swabs may cause discomfort, irritation, or a gagging sensation.

Stool Collection: Providing a stool specimen might make the subject feel embarrassed.

Urine Test: Female who could become pregnant, providing urine for a pregnancy test might feel embarrassed.

Questionnaires: Completion of a questionnaire and the questions might make the subject feel uncomfortable or upset.

Others:

Pregnancy: There are no data with this drug in pregnant women to inform a drug-associated risk. No teratogenicity or fetotoxicity was observed in animal reproduction studies with administration of nitazoxanide to pregnant rats and rabbits during organogenesis at exposures 30 and 2 times, respectively, the exposure at the maximum recommended human dose of 500 mg twice daily based on body surface area (BSA).

In the U.S. general population, the estimated background risk of major birth defects and miscarriage in clinically recognized pregnancies is 2% to 4% and 15% to 20%, respectively.

Breach of Confidentiality: Instances like lost or stolen laptops storing participant information, lost or stolen thumb drives, paperwork with subject PHI left unsecured may result in breach in confidentiality.

Unknown risks: Nitazoxanide and protocol mandated procedures may have risks previously unknown.

2.3.2 Known Potential Benefits

Given the limited clinical experience with nitazoxanide, there is no guarantee that subjects will receive direct benefit from participating in this study. It is possible that nitazoxanide will reduce the duration of symptoms secondary to Norovirus infection and may also reduce the duration of Norovirus shedding. There have been no prospective studies of Norovirus in the transplant setting and this study will allow a better assessment of the natural history of Norovirus in this setting. Lastly, collection of various immune response markers will allow assessment of the relative role of the host immune response and antiviral therapy to recovery from Norovirus infection in transplant recipients. All subjects will get the local standard of care provided to patients with Norovirus (i.e. antimotility agents and hydration).

3 OBJECTIVES

3.1 Study Objectives

A. Primary Objective:

1. To assess the *clinical efficacy* of nitazoxanide for the management of acute and chronic Norovirus in transplant recipients.

B. Secondary Objectives

1. To assess *virologic efficacy* of nitazoxanide
2. To assess the *safety* of nitazoxanide for the management of acute and chronic Norovirus in transplant recipients.

C. Exploratory Objectives

1. To assess *initial clinical improvement* in Norovirus Disease through 28 and 180 days.
2. To assess *markers of virologic improvement* Norovirus Disease through 28 and 180 days.
3. To assess the *contribution of immunologic response* to Norovirus to the clinical course of disease in treated and untreated subjects.
4. To define the *pharmacokinetics and dose response relationships* of nitazoxanide.
5. To define the *natural history* of Norovirus in nitazoxanide treated and untreated subjects.

3.2 Study Outcome Measures

No studies have been conducted to establish the optimal endpoint for assessing novel drugs for the treatment of Norovirus in immunosuppressed subjects. Further, there are no published FDA guidance documents to inform optimal endpoint selection for this indication.⁽¹⁾ Available literature and expert opinion was consulted to define proposed endpoints for this study.

3.2.1 Primary Outcome Measures

1. The time from randomization until initial clinical resolution of Norovirus symptoms for at least 48 hours through 180 days.

Clinical resolution will be assessed from the daily diary by the subject and will be defined as:

- a. Cessation of vomiting and,
- b. No stools classified by the Bristol Stool Chart as diarrhea (Type 6 or 7)

3.2.2 Secondary Outcome Measures

Virologic Efficacy

1. Time from randomization to first negative viral load through 180 days.
2. The change in viral titer between Day 1 and 180.

Safety

3. Incidence of unsolicited non-serious adverse events (see section 9 for details) through 60 days.
4. Incidence of laboratory adverse events (WBC, Hemoglobin, Platelet Count, Creatinine, Alkaline Phosphatase, ALT, AST, BUN and Bilirubin) through 60 days.
5. Incidence of protocol-specified serious adverse events (see section 9 for details) through 60 days.
6. Incidence of Hospitalization through 60 days.

3.2.3 Exploratory Outcome Measures

Clinical Improvement;

1. Time from randomization to initial clinical improvement in Norovirus disease through 28 and 180 days for at least 48 hours, as defined by:
 - a. 50% reduction in number of episodes of vomiting and,
 - b. Improvement in PO intake, as judged by the subjects and,
 - c. 50% reduction in the number of episodes of diarrhea as classified by the subject by the Bristol Stool Chart as type 6 or 7 bowel movements.
2. Time from randomization to initial cessation of vomiting through Day 180 (recurrent vomiting will be considered disease recurrence unless determined to be due to another etiology [i.e. GVHD]).
3. Time from randomization to subject report of no loss of appetite that is maintained for 48 hours through Day 180 (measure will be first time that the subject reports that they have no “loss of appetite” on their daily diary).
4. Time from first dose to initial cessation of diarrhea through Day 180 classified by the Bristol Stool Chart as type 6 or 7 bowel movements (recurrent diarrhea will be considered disease recurrence unless determined to be due to another etiology [i.e. GVHD]).
5. Time from randomization to 50% reduction in the amount of antimotility agents utilized by the subject through Day 180
6. Number of days of diarrhea through Days 28 and 180.
7. Number of stools classified by the Bristol Stool Chart as type 6 or 7 bowel movements through Day 28.
8. Number of days of IV hydration or total parenteral nutrition (TPN) therapy through Day 28.

9. Total number of days of hospitalization through Days 28 and 180.
10. Change in patient-reported quality of life as measured by EuroQOL-5 (global) and IBSQOL (diarrhea specific) [adult] or EuroQOL-5 Peds (global) and PedsQL GI Module [children] from baseline to Day 180.
11. Change in patient-reported physical function as measured by NIH PROMIS Physical Function (Adult) Pediatric Global Health (Peds) from baseline to Day 180.
12. Change in patient-reported emotional distress as measured by the NIH PROMIS Depression, Anxiety, Fatigue (Adult and Peds) from baseline to Day 180.
13. Change in patient-reported gastrointestinal symptoms as measured by the NIH PROMIS GI (Adult and Peds) symptoms (6 of 8 subscales) from baseline to Day 180.
14. The effect of co-pathogens, as determined by the BioFire stool pathogen screen, on the primary outcome measure.
15. Time from randomization until initial clinical resolution of Norovirus symptoms for at least 48 hours through Day 180. Clinical resolution will be assessed from the daily diary by the subject and will be defined as cessation of vomiting and no stools classified by the Bristol Stool Chart as diarrhea (Type 6 or 7) from the total population compared to the subgroup of subjects who do not report chromaturia (discoloration of urine) based on unsolicited self-reporting.
16. Incidence of unsolicited non-serious adverse events (see section 9 for details) through 60 days, laboratory adverse events (WBC, Hemoglobin, Platelet count, Creatinine, Alkaline Phosphatase, ALT, AST, BUN and Bilirubin) through 60 days, protocol-specified serious adverse events (see section 9 for details) through 60 days, and Hospitalization through 60 days from the total population compared to the subgroup of subjects who do not report chromaturia (discoloration of urine) based on unsolicited self-reporting.

Virologic Improvement:

17. Time to ≥ 1 log reduction in stool Norovirus genome copies.
18. Change in quantitative Norovirus load in the stool between Day 1 and Day 7, 14, 21, 28, 60, 120, and 180.
19. Change in Norovirus sequence from Day 1 to Days 28 and 60.
20. The effect of co-pathogens, as determined by the BioFire stool pathogen screen, on the time from the randomization to first negative viral load through 180 days.
21. Time from the randomization to first negative viral load through 180 days and the change in viral titer between Day 1 and 180 from the total population compared to the subgroup of subjects who do not report chromaturia (discoloration of urine) based on unsolicited self-reporting.

Immunologic Response:

22. Change in Norovirus-specific serum and stool IgA, IgM and IgG between Day 1 and Day 28 and 60 (stool only).
23. Association between change in total lymphocyte count and T cell subsets at Day 1 and 180 and clinical resolution of Norovirus symptoms.
24. Association between change in total lymphocyte count and T cell subsets at Day 1 and 180 and undetectable quantitative norovirus PCR.
25. Association between change in Norovirus-specific serum and stool IgA, IgM and IgG from Day 1 to Days 28 and 60 (stool only) and clinical resolution of Norovirus symptoms.
26. Association between change in Norovirus-specific serum and stool IgA, IgM and IgG from Day 1 to Days 28 and 60 (stool only) and undetectable quantitative Norovirus PCR.

Pharmacokinetics and Dose Response:

27. For subjects consenting to PK draws, concentrations of nitazoxanide metabolites (tizoxanide and tizoxanide glucuronide) 1 to 4 hours after the first dose on Day 7 and 10 minutes before the second dose on Day 21.

Natural History of Disease:

28. Time to allograft rejection as per each center team
29. Time to allograft loss as reported to UNOS.
30. Time to death.
31. Time to withdrawal from the study because of intolerance or drug related adverse events.
32. Correlation of secretor status as defined by phenotype and genotype, separately, and clinical resolution of Norovirus as defined by the primary endpoint.

4 STUDY DESIGN

The study will be a phase 2 multi-center double-blind placebo-controlled study of the efficacy and safety of nitazoxanide for the treatment of solid organ and hematopoietic stem cell transplant recipients with symptomatic diarrhea due to Norovirus. The study will involve approximately 160 subjects randomly assigned (1:1) to nitazoxanide or placebo. The study duration is 60 months and subject participation duration is 6 months. Given the safety of prolonged therapy with nitazoxanide, lack of interactions with common post-transplant medications, putative antiviral activity and prolonged duration of viral shedding we are assessing 56 doses of therapy. The longitudinal monitoring phase will provide useful information on the course of host and viral responses in subjects with chronic Norovirus infection with and without treatment.

The primary endpoint

is to determine the *clinical efficacy* of nitazoxanide that will be assessed as the time from randomization until clinical resolution of Norovirus symptoms for at least 48 hours, assessed through 180 days. Secondary endpoints include *virologic efficacy* of nitazoxanide that will be assessed as the time from randomization to first negative viral load through 180 days and by comparing the change in viral titer between Day 1 and 180; *safety* of nitazoxanide that will be assessed by the frequency of adverse events and serious adverse events.

There are 2 arms of the study:

Nitazoxanide Arm: All subjects age ≥ 12 years: 500 mg (one tablet) nitazoxanide by mouth twice daily with food for 56 consecutive doses.

Placebo Arm: All subjects age ≥ 12 years: Placebo (one tablet) by mouth twice daily with food for 56 consecutive doses.

5 STUDY ENROLLMENT AND WITHDRAWAL

Approximately 160 males and females ≥ 12 years of age inclusive, who meet all eligibility criteria will be enrolled. All candidates at all centers that are eligible to be included in the studies will be offered the opportunity to participate in the trial. Study subjects are seen in patient or clinic setting and have either community onset or hospital acquired disease.

5.1 Subject Inclusion Criteria

Subjects should meet all of the following inclusion criteria

1. Male or female age ≥ 12 years.
2. Recipient of a solid organ or hematopoietic stem cell transplant.
3. Positive test result for Norovirus within 14 days of enrollment that is obtained as part of routine clinical care using a Norovirus testing available to the site.
4. Active GI symptoms (diarrhea or vomiting) that, in the opinion of the PI, are secondary to Norovirus.[#]
5. Willing and able to provide written informed consent and assent before initiation of any study procedures, consistent with local IRB policy.
6. Subjects must be of non-childbearing potential or if of childbearing potential, must be using an effective method of birth control or must be abstinent.
 - Non-childbearing potential is defined as surgically sterile or postmenopausal for $>$ one year.
 - Effective methods of birth control include the use of hormonal or barrier birth control such as implants, injectable contraceptives, combined oral contraceptives, intrauterine devices [IUDs] or condoms with spermicidal agents during study period. Female subjects must be using an effective method of birth control or practice abstinence and must agree to continue such precautions during the study and for 30 days after the Day 28 study visit.
 - A woman is eligible if she is monogamous with a vasectomized male. This subject is considered low risk and not required to use contraception.
7. Agrees to complete all screening requirements, study visits and procedures.

[#] Patients must have active diarrhea, which is defined as at least 3 days of Bristol 6 or 7 stools in the past 2 weeks prior to enrollment per patient report.

5.2 Subject Exclusion Criteria

Subjects meeting any of the exclusion criteria at baseline will be excluded from study participation

1. Other identified infectious causes of diarrhea at screening*.
2. Any condition that would, in opinion of the Site Investigator, place the subject at an unacceptable risk of injury or render the subject unable to meet the requirements of the protocol.
3. Subjects receiving oral or intravenous immunoglobulin therapy concurrently or in the 14 days prior to enrollment.
4. Nitazoxanide use for any illness in the previous 30 days prior to randomization.
5. Have received experimental products within 30 days prior to the study entry or plan to receive experimental products at any time during the study
6. Known sensitivity to nitazoxanide or any of the excipients comprising the nitazoxanide tablets.
7. Subjects unable to swallow oral medications.
8. Subjects with ostomy.
9. Women who are pregnant or lactating or have a positive urine pregnancy test at screening/enrollment/Day 1.

Co-enrollment in other studies is allowed if none of the above exclusion criteria are met.

*Alternative diagnosis requiring treatment would be considered a co-infection; if the testing is positive for a pathogen that the PI does not feel is causing the symptoms, they may be included but the PI or his/her designee must document that the positive test is not clinically significant, does not require treatment and is not causing the symptoms making the patient eligible for enrollment.

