6 STUDY INTERVENTION/INVESTIGATIONAL PRODUCT

6.1 Study Product Description

Nitazoxanide is a synthetic antiprotozoal agent for oral administration. It is designated chemically as 2-acetyloxy-N- (5-nitro-2-thiazolyl) benzamide. The molecular formula is $C_{12}H_9N_3O_5S$ and the molecular weight is 307.3. The placebo will look identical to nitazoxanide, and will have the same inactive ingredients (described in section 6.1.2).

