6.1.2 Formulation, Packaging, and Labeling

Nitazoxanide Tablets

Nitazoxanide will be supplied as a 500 mg round, yellow, film-coated tablet with “CTM” imprint, manufactured by Romark, L.C. Per the package insert, inactive ingredients include: maize starch, pregelatinized corn starch, hydroxypropyl methylcellulose, sucrose, sodium starch glycollate, talc, magnesium stearate, soy lecithin, polyvinyl alcohol, xanthan gum, titanium dioxide, FD&C Yellow No. 10 Aluminum Lake, FD&C Yellow No. 6 Aluminum Lake, and FD&C Blue No. 2 Aluminum Lake.

Placebo Tablets

Placebo will be supplied as a matching tablet of the active drug which will also be a round, yellow, film-coated tablet with “CTM” imprint. Ingredients include: lactose monohydrate, magnesium stearate, talc, soy lecithin, polyvinyl alcohol, xanthan gum, titanium dioxide, FD&C

Yellow No. 10 Aluminum Lake, FD&C Yellow No. 6 Aluminum Lake, and FD&C Blue No. 2 Aluminum Lake. In order to maintain the blind, the placebo will be formulated for the same appearance as the active study drug.

Package and Labeling

All study product will be packaged in two 60cc identical containers each containing 30 tablets. Each container will also be labeled in compliance with applicable regulatory requirements, including the FDA-required cautionary statement “*Caution: - New drug -Limited by Federal Law to Investigational Use.*”

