4.4. Treatments

4.4.1. Treatments Administered

Subjects will be randomized to receive either one 500 mg tablet of nitazoxanide twice daily with food for 56 consecutive doses, or placebo. Nitazoxanide is a synthetic antiprotozoal agent for oral administration. The placebo will look identical to nitazoxanide and will have the same inactive ingredients.

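### The placebo is described as having the same inactive ingredients as nitazoxanide, but the ingredient lists differ, and exclusion 6 does not cover the placebo's own excipient, lactose monohydrate

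*Protocol*

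**What the plan says.** Protocol 6.1 states: "The placebo will look identical to nitazoxanide, and will have the same inactive ingredients (described in section 6.1.2". SAP 4.4.1 repeats it: "The placebo will look identical to nitazoxanide and will have the same inactive ingredients".

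Protocol 6.1.2, to which 6.1 refers, then gives two different lists. For the active tablet, "inactive ingredients include: maize starch, pregelatinized corn starch, hydroxypropyl methylcellulose, sucrose, sodium starch glycollate, talc, magnesium stearate", followed by film-coat components and three dyes. For the placebo, "Ingredients include: lactose monohydrate, magnesium stearate, talc, soy lecithin, polyvinyl alcohol, xanthan gum, titanium dioxide", followed by the same three dyes. SAP 4.4.2 reproduces both lists. Protocol 2.1 also lists the active tablet's inactive ingredients, again without lactose.

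Exclusion 6 in Protocol 5.2, repeated in SAP 4.3, covers "Known sensitivity to nitazoxanide or any of the excipients comprising the nitazoxanide tablets". No criterion names the placebo's excipients or lactose. The nearest is exclusion 2: "Any condition that would, in opinion of the Site Investigator, place the subject at an unacceptable risk of injury", or a condition that leaves the subject unable to meet the protocol's requirements.

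The placebo regimen in Protocol section 4 is "Placebo (one tablet) by mouth twice daily with food for 56 consecutive doses".

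**The concern.** Exclusion 6 screens fully for excipient sensitivity only if the two tablets share their excipients. Protocol 6.1 says that they do, and Protocol 6.1.2 shows that they do not. A site applying exclusion 6 as written is not asked about the one ingredient found only in the placebo. A site relying on 6.1 has no prompt to consider it under exclusion 2.

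Two things are at stake. The first is screening: subjects with a known sensitivity should not be assigned, by chance, to a tablet that contains the substance. The second is interpretation. The primary event in Protocol 3.2.1 requires no Bristol 6 or 7 stools, so an inactive ingredient that loosened stools in one arm would act on the endpoint itself. Two exploratory outcomes in Protocol 3.2.3, days of diarrhea through Day 28 and number of type 6 or 7 stools through Day 28, have windows that nearly coincide with dosing. Adverse event data would not reveal a mild problem, because Protocol 9.2.1 records non-serious clinical events only if they lead to modification or discontinuation of study drug.

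**Working it through.** **Step 1: compare the lists (Protocol 6.1.2; SAP 4.4.2 is identical).**

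| Where listed | Ingredients | Count |
|---|---|---|
| Both tablets | talc; magnesium stearate; soy lecithin; polyvinyl alcohol; xanthan gum; titanium dioxide; three dyes | 9 |
| Placebo only | lactose monohydrate | 1 |
| Active only | sucrose; maize starch; pregelatinized corn starch; sodium starch glycollate; hydroxypropyl methylcellulose | 5 |

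Active tablet: 9 + 5 = 14 inactive ingredients. Placebo: 9 + 1 = 10. The statement that they are the same is wrong in both directions.

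**Step 2: apply the criteria to a subject with known lactose sensitivity.** Lactose is not among the 14 excipients of the nitazoxanide tablet, so exclusion 6 is not met. None of the other criteria names lactose. Exclusion 2 applies only if the investigator judges the risk unacceptable or the subject unable to meet the protocol's requirements.

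**Step 3: exposure.** The lactose content per tablet is not given. Assuming 0.1 to 0.5 g per tablet, two tablets a day give 0.2 to 1 g a day. The documents give no amount at which symptoms would be expected, so this is a range of exposure and not of effect.

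**Step 4: what a placebo-arm effect could do to the primary test.** The plan gives no figure for this, so an illustration was run. Inputs from Protocol 11.1 and 11.2: 64 per arm, medians of 135 days (placebo) and 67.5 days (nitazoxanide), 180 days of follow-up, log-rank test at 5% two-sided. Assumptions: exponential times, and a fraction f of placebo subjects unable to resolve during the 28 days of dosing; 5,000 runs per setting.

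| f (assumed) | Rejection rate, no drug effect (two-sided) | Power, planned effect |
|---|---|---|
| 0% | 5.5% | 91.4% |
| 5% | 4.7% | 90.8% |
| 10% | 5.0% | 91.1% |
| 20% | 4.9% | 92.1% |
| 30% | 4.9% | 92.9% |

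The 91.4% at f = 0 agrees with the 91.3% in the plan's own power table when no one is re-treated. Simulation error is about √(0.05 × 0.95 / 5000) = 0.3 points in the first rate column and √(0.914 × 0.086 / 5000) = 0.4 points in the second. With no drug effect, rejections in favor of nitazoxanide went from 2.7% at f = 0 to 2.5% at f = 30%, so they did not rise.

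The effect is small because few placebo subjects would resolve that early under the planning assumption: 1 − 2^(−28/135) = 13.4%. At f = 30%, only 0.30 × 13.4% = 4.0% of the arm is delayed, or about 64 × 0.040 = 2.6 subjects. Faster placebo resolution than planned would enlarge this. The illustration does not cover the Day 28 exploratory outcomes.

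**Step 5: the trial as it stands.** SAP 6.6 reports 31 subjects enrolled. At 1:1 that is 15 or 16 per arm, so one placebo subject is 1/16 = 6.3% to 1/15 = 6.7% of the arm. This is a share of the arm and not an estimated effect.

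**The case against.** A reader might infer that the placebo can itself cause diarrhea and so biases the trial toward nitazoxanide. The documents do not support that. They give neither the lactose content nor a threshold for symptoms, and nowhere say that these tablets loosen stools. A reader might also infer that excipient effects can run only one way. That does not follow either: five excipients are found only in the active tablet, and exclusion 6 removes only known sensitivity to them. Protocol 2.1 also reports diarrhea in 2.1 to 4.2% and vomiting in 1.1% with nitazoxanide itself, which would act on the same endpoint in the other direction. These objections stand, and the illustration found little effect even on generous assumptions.

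Exclusion 2 gives an investigator room to exclude a subject with a serious reaction to lactose. That stands, so such a subject is not excluded by exclusion 6 but is not necessarily eligible. It is weaker than a named criterion, because it depends on the investigator knowing what the placebo contains.

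Both ingredient lists are introduced as inclusive, and the active list is taken from the package insert, so the absence of lactose from the active tablet is strictly an inference. It is a reasonable one: Protocol 2.1, Protocol 6.1.2 and SAP 4.4.2 all agree, and 6.1 names 6.1.2 as its source.

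With enrollment stopped, rewording an exclusion cannot change who entered this trial. That also stands and shapes the fix. Nor would the rewording reach unrecognized intolerance.

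**Conclusion.** The contradiction between Protocol 6.1 and 6.1.2, and between SAP 4.4.1 and 4.4.2, is established from the text. So is the resulting gap: no specific criterion screens for known sensitivity to the ingredient found only in the placebo, to which half of subjects are assigned for up to 56 scheduled doses. This rests on reading the printed lists as complete for lactose.

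Any effect on Bristol 6 or 7 stools remains a possibility that depends on an unstated lactose content. It cannot be sized from the documents. For the primary test at the planned 64 per arm it is probably small: power moved from 91.4% to 92.9% even with an assumed 30% of placebo subjects unable to resolve during dosing, and the false-positive rate stayed near 5%. That result was not obtained at 31 subjects and depends on the planned placebo median of 135 days. The point is therefore one of inaccurate description and incomplete screening, not of demonstrated bias.

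**What to change.** 1. Reconcile the passages: change Protocol 6.1 and SAP 4.4.1 to say that the placebo matches nitazoxanide in appearance but differs in inactive ingredients, and refer to the two lists.
2. Have exclusion 6, in Protocol 5.2 and SAP 4.3, refer to the excipients of either study product, nitazoxanide or placebo.
3. Carry the corrected description into the clinical study report, so that the placebo is not reported as having identical excipients. If the manufacturer can supply the lactose content per tablet, state it there.
4. From the medical history already collected (SAP Listing 7, which is sorted by treatment group), identify by arm any enrolled subject with lactose intolerance and report the count. This finds only recorded intolerance.

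Items 1, 3 and 4 need text changes and one pass through an existing listing, with no new data. Item 2 cannot affect the 31 subjects already enrolled; if the protocol is used again, it would cost a few more screen failures.
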